1 PROTOCOL SUMMARY

1.1 SYNOPSIS

Title: Advanced a/LCI Systems for Improved Clinical Utility: An Optical Coherence Tomography (OCT) Pilot Study (OCT Pilot)

Study Description: This is a pilot study to test the operating characteristics of a newly developed dual modality probe including optical coherence tomography (OCT) and angle-resolved low-coherence interferometry (a/LCI) in human subjects, and to collect data for further optimization of the a/LCI-OCT device. Phase I will incorporate the single modality OCT probe. Phase II will consist of a dual modality probe to include both OCT and a/LCI components.

Potential subjects will be presenting to a UNC Endoscopy unit for routine upper endoscopy (EGD) for clinical signs or symptoms. If eligible, informed consent will be obtained prior to undergoing this routine care upper endoscopy. During the endoscopy, and prior to taking any biopsies, the probe will be attached to the end of the endoscope and passed with the endoscope into the esophagus. The probe will make contact with the epithelium of the esophagus, and data will be collected as part of this research study to identify operating characteristics of the new OCT device and the a/LCI-OCT combined device. Esophageal images and pictures will be obtained during the procedure and will be used in this study. If biopsies are taken for routine care (clinical biopsies), then results from those biopsies will be used in this study. For a subset of subjects, participating in the combined-modality probe, study-specific biopsies will be taken at the same location the probe is deployed, to allow comparison of data from the imaging modalities to “gold-standard” biopsy data. Additionally, slides may be requested from clinical biopsies for use in this study after they have yielded their results for routine care.

Objectives: To test a newly developed imaging device in human subjects to determine 1) whether adequate tissue contact can be attained to acquire high quality images, and 2) to identify if these images can discern whether the imaged tissue is squamous or Barrett's Esophagus (BE) epithelium.

Endpoints: None

Study Population: Patients of UNC Healthcare undergoing routine care endoscopy with or without Barrett's Esophagus. Target enrollment includes two cohorts, with an approximate enrollment of up to 82 subjects. Cohort A will consist of 14 subjects in each of 3 groups; normal asymptomatic controls, non-dysplastic Barrett's Esophagus, and

history of or current dysplastic Barrett's Esophagus (High Grade Dysplasia (HGD) or Low Grade Dysplasia (LGD)). Cohort B will consist of 20 patients in each of the two groups; current dysplastic Barrett's Esophagus of either High Grade Dysplasia (HGD) or Low Grade Dysplasia (LGD)) and normal controls (with or without history of previous successful esophageal ablation). Classification of patients will occur based on medical history and clinical pathology obtained during the EGD.

Description of Sites/Facilities
Enrolling Participants:

UNC Chapel Hill (Enrolling Site)
Duke University (Device Manufacture)

Description of Study Intervention:

The purpose of this instrument is to obtain optical measurements from the esophageal mucosa via an endoscopic probe. The modalities used by this probe are angle-resolved low-coherence interferometry (a/LCI) and Optical Coherence Tomography (OCT); depth-resolved optical imaging technology. These optical readings provide indications of subsurface tissue architecture and will assist in the detection and diagnosis of metaplastic and dysplastic conditions such as Barrett's esophagus.

The probe is designed to be used in conjunction with the visual guidance provided by a commercial endoscope. The probe has mechanical features similar to a radiofrequency ablation (RFA) "paddle", which is externally attached to an endoscope to provide ablative therapy under visual guidance of the endoscope.

[figure not shown]
Once inserted into a patient's esophagus and placed against the tissue surface, the probe will acquire 2D OCT images of the tissue surface at operator-selected locations. Some of the optical data received will be displayed in real-time. All optical data will also be stored on a computer for post hoc analysis.

During Phase I the OCT instrument will be used alone. The components of the OCT device are grouped into the following modules: 1) Optical probe, 2) OCT engine, 3) computer system and 4) physical enclosure. Phase II of the study will consist of a dual modality a/LCI - OCT combined probe. The combined probe will consist of the following modules: 1) Optical probe, 2) OCT engine, 3) a/LCI engine, 4) computer system and 4) physical enclosure. See section 6.1 for detailed device descriptions.

Study Duration: 24 Months

Participant Duration: 7 days

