5 STUDY POPULATION

5.1 INCLUSION CRITERIA

Subjects must meet all of the following criteria to be eligible for this study:

1. Presenting to UNC for routine care upper endoscopy
2. Meet one of the following criteria:
 - 2.1. Cohort A
 - 2.1.1. Presenting to UNC for upper endoscopy of GI conditions without esophageal symptomatology with no history of gastroesophageal reflux disease (GERD) or other esophageal condition affecting the epithelium (asymptomatic controls). Esophageal

symptomology includes, but is not limited to, heartburn, globus, chest pain, dysphagia, and odonophagia OR,

- 2.1.2. Current dysplastic or non-dysplastic Barrett's Esophagus of any length OR,
- 2.1.3. History of dysplastic or non-dysplastic Barrett's Esophagus after treatment with endoscopic eradication therapy (EET)

OR

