9 STATISTICAL CONSIDERATIONS

9.1 STATISTICAL HYPOTHESES

No hypothesis tests will be performed. All statistical estimates (e.g., proportions, incidence rates, sensitivity, specificity, means, correlations, etc.) will be tabulated with 95% confidence intervals (CIs).

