9.2 SAMPLE SIZE DETERMINATION

Cohort A will be imaged with OCT. Previous data on OCT demonstrate that established systems are sensitive with respect to detecting Barrett's mucosa. For instance, Poneros et al (2001) found a 97% sensitivity rate using OCT in 38 patients²⁹. At this stage of development, if we can achieve at least 70% sensitivity, then the device will pass initial testing. If optimal sensitivity is 95%, and the lowest acceptable sensitivity is 70%, then we will require at least 14 patients with evaluable data in each group (42 total in Cohort A) to assess whether the device adequately meets this threshold with 85% power.

Cohort B will be imaged with a/LCI. Our group previously conducted and published a study in 2011 using single-point a/LCI to measure nuclear diameter as an indicator of dysplasia in the esophagus.¹³ The primary differentiating characteristic between dysplastic and normal tissue was nuclear diameter (measured by a/LCI). For dysplastic tissue, the mean nuclear diameter and standard deviation was $13.0 \pm 1.1 \mu\text{m}$, and for normal tissue, the same respective values were $10.3 \pm 1.7 \mu\text{m}$. This difference was highly statistically significant, and we rejected the null hypothesis (no difference between normal and dysplastic nuclear diameters) with a p-value of 0.0001.

To determine the number of targeted patient enrollments in Cohort B, we conducted a statistical power analysis based on our previous results. For a sample size of 20 patients with dysplasia and 20 patients with normal esophageal tissue, and targeting the same p-value of 0.0001, we expect a robust statistical power of 97% when conducting a two-sample t-test for nuclear diameter distributions matching our observations from the 2011 study. We would therefore expect a 97% chance of validating our previous observations at the same level of significance for a sample size of 20. Comparatively, for a sample size

of 10 patients in each category, our power would be only 36%, far too low; for a sample size of 30 patients in each category, our power would be greater than 99.9%, which is unnecessarily high. Therefore, for Cohort B, we will target 20 patients with dysplasia and 20 normal patients to achieve a strong statistical power without an undue excess in patient enrollment.

To accommodate Cohort B, which will be receiving the dual modality a/LCI-OCT probe, we have therefore changed the sample size to be a total of 82 (42 in Cohort A, and 40 in Cohort B).

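### Cohort A's third group may include treated patients with no columnar mucosa left, so 14 per group and 85% power for Barrett's sensitivity are not secured

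*Combined protocol and SAP*

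**What the plan says.** Cohort A has three groups of 14: asymptomatic controls, non-dysplastic Barrett's, and a third group described in Section 1.1 as "history of or current dysplastic Barrett's Esophagus". Section 5.1, criterion 2.1.3, admits to Cohort A patients with a "History of dysplastic or non-dysplastic Barrett's Esophagus after treatment with endoscopic eradication therapy (EET"). Neither section asks for residual columnar mucosa.

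Section 9.2 argues from the observation that "established systems are sensitive with respect to detecting Barrett's mucosa". It sets the targets with "If optimal sensitivity is 95%, and the lowest acceptable sensitivity is 70" per cent, and concludes that "we will require at least 14 patients with evaluable data in each group (42 total in Cohort A"). The stated purpose of that number is "to assess whether the device adequately meets this threshold with 85% power". No test level or sidedness is given, and Section 9.1 says "No hypothesis tests will be performed".

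Section 9.4 classifies each imaging site as columnar or squamous, with endoscopy as the reference. It defines sensitivity as the share of sites that the device classifies correctly, without limiting this to columnar sites. Section 9.3 defines an enrolled subject by successful use of the device and evaluable data, and does not say what makes data evaluable for sensitivity.

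For Cohort B, Section 1.1 allows "normal controls (with or without history of previous successful esophageal ablation"), with no limit on what was ablated. In Section 5.1, criterion 2.2.3 describes the asymptomatic controls as never having had dysplastic Barrett's, and criterion 2.2.2 admits treated patients separately.

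**The concern.** Sensitivity for Barrett's mucosa can be estimated only where there is Barrett's mucosa to detect. A patient whose dysplastic Barrett's was fully eradicated fits the wording of Cohort A's third group but may offer only squamous sites. That patient informs specificity, yet nothing in the plan stops the patient from filling one of the 14 places on which the 85% depends.

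Section 9.2 treats 70% sensitivity as the level at which the device passes initial testing, and the 85% is the reason given for enrolling 42 patients in Cohort A. If the third group ends with fewer than 14 patients who have columnar tissue, its share of that reasoning no longer holds, and the group cannot be re-composed once enrolment is complete.

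**Working it through.** **Inputs.** From Section 9.2: lowest acceptable sensitivity p0 = 0.70, optimal sensitivity p1 = 0.95, n = 14 evaluable patients per group, power 85%. Assumed, because the plan does not state it: one result per patient and an exact binomial test at one-sided 5%. Also not given: the number m of the 14 third-group patients who have a columnar imaged site. It is varied below.

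**Reproducing the plan.** Pass if at least 13 of 14 are correct.

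- Alpha = 14 × 0.7^13 × 0.3 + 0.7^14 = 0.0407 + 0.0068 = 0.0475.
- Power = 14 × 0.95^13 × 0.05 + 0.95^14 = 0.3593 + 0.4877 = 0.847.

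This matches the stated 85%. Other readings at n = 14 do not: exact one-sided 2.5% gives 48.8%, and the normal approximation gives 79.8% (one-sided 5%) or 56.8% (two-sided 5%). The figure is sound if all 14 patients supply a columnar result.

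**With m columnar patients.** For m from 9 to 13, allowing one miss breaks the 5% limit, so the rule becomes no misses, with alpha = 0.7^m and power = 0.95^m. The last two columns show what happens if one miss is still allowed.

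| m | Rule at one-sided 5% | Alpha | Power | Alpha, at most one miss | Power, at most one miss |
|---|---|---|---|---|---|
| 14 | 13 of 14 | 0.047 | 84.7% | 0.047 | 84.7% |
| 13 | 13 of 13 | 0.010 | 51.3% | 0.064 | 86.5% |
| 12 | 12 of 12 | 0.014 | 54.0% | 0.085 | 88.2% |
| 10 | 10 of 10 | 0.028 | 59.9% | 0.149 | 91.4% |
| 9 | 9 of 9 | 0.040 | 63.0% | 0.196 | 92.9% |
| 8 | none | – | – | 0.255 | 94.3% |

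At m = 8 even a perfect result has probability 0.7^8 = 5.8% under p0, so nothing can pass at 5%; the same holds for smaller m. The rise in power from 13 down to 9 is a product of discreteness: fewer patients have to be flawless.

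**Uncertain m.** If each third-group patient independently lacks columnar tissue with an assumed probability of 10%, 25% or 50%, average power at one-sided 5% is 61%, 52% or 13%.

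**Pooling the two Barrett's groups.** This assumes that all 14 non-dysplastic patients have columnar sites. With 7 more from the third group (21 in all), the rule is 19 of 21 and power is 91.5%. With 14 more (28 in all), it is 24 of 28 and 98.8%. With only 1 to 4 more, pooled power is 77% to 83%.

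**Controls.** The asymptomatic group is expected to have no columnar mucosa, so its 14 patients add to specificity only.

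**The case against.** Several points on the other side have force.

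- Section 9.2 asks for 14 patients with evaluable data, which could be read as requiring a columnar site. But Section 9.3 does not define the term that way.
- Section 8.1.2.1 has the probe placed on both normal and columnar tissue, and Section 7.2 lets the investigator withdraw and replace a participant. The first cannot be done where no columnar tissue remains. The second sets no rule for this case, since such a patient is eligible under 2.1.3, and it would discard the squamous data.
- Read literally, the sensitivity in Section 9.4 counts all sites, so squamous-only patients would contribute. That quantity is overall agreement. It would let squamous sites stand in for detecting Barrett's.
- Section 9.1 rules out hypothesis tests, and much of the loss in the table comes from holding a discrete test strictly to 5%. This stands: if one miss is still allowed, power holds and the false-pass risk rises instead. The stated combination is missed either way.
- Pooling, or several sites per patient, could keep the power. The plan states its figure per group, and specifies neither pooling nor a way to handle several sites within a patient.

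A reader might go further and infer that the opposite placement of ablated patients (third group in Cohort A, possible normal in Cohort B) makes results pooled across cohorts inconsistent. The documents do not support this. Section 9.4 works by site, so a squamous site is squamous whatever the patient's label, and Section 9.3 combines cohorts only for device optimization. The two cohorts also ask different questions.

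**Conclusion.** The 85% power is not secured for Cohort A's third group. It would be too strong to say that it is not delivered. Eradication therapy does not imply that no columnar mucosa remains, and the documents give no count of patients without it, so the figures for m below 14 are scenarios. Nor are all treated Barrett's patients affected: the third group covers a history of dysplastic disease only, and the problem arises only for those whose imaged sites are all squamous.

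Within those limits there is no slack. At an assumed exact one-sided 5%, one such patient takes the group's power from 84.7% to 51.3%, and six leave 14 − 6 = 8, where no result can pass. If one miss is still allowed, the false-pass risk rises to 0.085 at 12 and 0.149 at 10.

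The two descriptions of Cohort B's normal controls, in Section 1.1 and criterion 2.2.3, are a separate inconsistency and must be reconciled. In a pilot that reports intervals this does not undermine the study, but it should be corrected because the sensitivity threshold decides whether the device moves on.

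**What to change.** In Sections 1.1 and 9.2, state that only patients with at least one endoscopically columnar imaged site count toward the 14 in each Barrett's group, and that treated patients with squamous sites only contribute to specificity. Alternatively, restate the power for the pooled Barrett's patients with columnar sites (91.5% at 21, 98.8% at 28). Either way, give the test level and pass rule behind the figure, and say that the 14 controls serve specificity.

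In Section 9.4, compute sensitivity on columnar sites and specificity on squamous sites. Reconcile Section 1.1 with criterion 2.2.3 on who is a Cohort B normal control.

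The cost is protocol wording. Under the first option the third group may fill slightly more slowly; under the second the stated power changes.

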1.2 SCHEMA

1.3 SCHEDULE OF ACTIVITIES (SOA)

Procedures ⁷	Screening ¹	Enrollment ¹	Post-EGD	7 Day Follow-Up (+/-3 days)
Informed consent	X			
Eligibility Assessment	X	X		
Demographics	X			
Medical history	X			
Urine Pregnancy Test		X ²		
Routine Care EGD		X ³		
Esophageal Images		X		
Research Biopsies		X ⁶		
Administer Probe		X ⁵		
Collection of Pathology Results			X ⁴	
Adverse event review and evaluation	X	X		X
Complete Case Report Forms (CRFs)	X	X	X	X

¹Screening and enrollment can occur on the same day

²Urine pregnancy tests will be performed on females with reproductive potential.

³EGD is performed as part of routine care. Subjects would be receiving this EGD regardless of participation in the study.

⁴Only if biopsies are taken for routine clinical care during the procedure. If biopsies are taken for routine clinical care during this procedure, then pathology results will be collected as part of this study, and slides may be requested from clinical biopsies for use in this study after they have yielded their results for routine care.

⁵Probe utilized can be either the OCT probe (Cohort A) or the combined a/LCI-OCT probe (Cohort B), based on Investigator discretion at time of enrollment.

⁶ Research biopsies may be taken for participants in Cohort B, per discretion of principal investigator.

⁷ Both cohorts (A and B) will follow the same schedule of activities, unless specifically mentioned otherwise.

2 INTRODUCTION

2.1 BACKGROUND

Barrett's esophagus (BE) is a metaplastic change where the normal squamous epithelium of the esophagus is replaced by intestinal columnar epithelium, typically in response to chronic gastroesophageal reflux.^{1, 2} BE is a known risk factor for esophageal adenocarcinoma (EAC)³, a cancer with a high mortality rate and rapidly increasing incidence in developed countries.^{4, 5} The increased risk of cancer in BE patients leads to a need for surveillance, via endoscopy with random biopsies scattered across the affected tissue, using a biopsy pattern termed the "Seattle protocol".⁶ However, this pattern samples <5% of BE tissue, leading to substantial sampling error. In spite of evidence that endoscopic surveillance does not substantially impact cancer mortality,⁷ it is still the recommended management tool for in BE patients, due to a lack of proven alternatives.⁸

Because of this problem with sampling error, many optical techniques have been proposed for improving detection of pre-cancerous, dysplastic BE tissues but none have yet been widely adopted for routine use,⁸ due primarily to limited performance. While high resolution methods, such as confocal microscopy, have shown good sensitivity and specificity, the need to manually move a point probe to scan large areas of epithelium limits clinical utility. In comparison, wide area imaging approaches, such as autofluorescence imaging, view more tissue area but offer lower sensitivity and specificity. Recently, Thekke and Richards-Kortum advocated a multi-modality approach for optimal cervical screening.⁹ Similar approaches have been suggested for BE screening as well.¹⁰ The Investigators seek to create a novel imaging platform embodying this approach. This platform combines wide area imaging, using optical coherence tomography (OCT) to visualize esophageal epithelial regions, with high resolution, depth-resolved measurements of nuclear morphology, using angle-resolved LCI (a/LCI) to provide highly sensitive and specific detection of dysplasia.

The Investigators seek to implement and test advanced optical systems for detection of dysplastic tissue in BE patients. The a/LCI technique is based on examining the angular distribution of light scattering to determine structural features in a biological sample.¹¹ The approach can be used as a diagnostic of early pre-cancerous changes (dysplasia) by measuring the size of cell nuclei in the basal layer of the epithelium.¹² In a preliminary *in vivo* study, a/LCI nuclear morphology measurements were shown to be an effective biomarker for detecting dysplastic tissues in BE patients,¹³ achieving 87.8% accuracy. Significantly, this biomarker has 100% negative predictive value (NPV), a strong justification for clinical use. The Investigators seek to improve the clinical utility of a/LCI by covering wider tissue areas and incorporating the visual guidance of OCT.

Angle-resolved LCI (a/LCI) and OCT are two imaging technologies that will be integrated into one probe. The purpose of the first phase of this pilot study is to utilize optical coherence tomography (OCT) technology alone. In the second phase of the study, the optical coherence tomography (OCT) technology will be combined with the angle-resolved LCI (a/LCI) into a multimodal device developed by investigators on a small population of patients in an effort to gather information necessary for continuing development as a screening tool described above.

2.2 STUDY RATIONALE

Esophageal adenocarcinoma (EAC) is a deadly disease which has been rapidly increasing in incidence.¹⁴ The rate of mortality from this cancer has remained above 80%,¹⁴ even as mortality and incidence of other types of gastrointestinal cancers, such as colon cancer¹⁵, have been decreased through improved screening programs.¹⁶ The leading risk factor for EAC is Barrett's esophagus (BE), a very common metaplastic tissue condition arising from gastroesophageal reflux disease (GERD)³ which is thought to be the precursor to this cancer. BE can progress to EAC through dysplastic changes,¹⁷ transitioning from non-dysplastic BE to low grade dysplasia (LGD), high grade dysplasia (HGD), and eventually EAC.¹⁸ The increased risk of EAC in BE patients justifies periodic surveillance via endoscopy with biopsy³. The difficulty of accurate identification of dysplasia in the epithelium requires clinical guidelines to recommend frequent surveillance endoscopy⁸. However, the endoscopic surveillance protocol is laborious,⁸ and nearly half of surveillance procedures do not adhere to guidelines.¹⁹ The net result is that current surveillance approaches are not particularly effective at preventing mortality.⁷ The need for more effective tools for preventing esophageal cancer in the setting of BE is urgent, especially given that 2-3 million Americans harbor this lesion.

Investigators seek to create a multimodal screening tool that combines *in situ* measurements of nuclear morphology, a proven biomarker of dysplastic progression²⁰, with an imaging modality that gives visual representation of the architecture of BE tissues.²¹⁻²⁴ Angle-resolved LCI (a/LCI) obtains accurate, high resolution nuclear morphology measurements using depth-gated light scattering measurements^{11,25}. Investigators have shown that a/LCI nuclear morphology measurements can detect dysplastic lesions *in vivo* in the esophagus²⁶ and *ex vivo* in other types of epithelia such as colon²⁷ and trachea²⁸ with high sensitivity and specificity. As a standalone modality, a/LCI is somewhat limited for clinical screening of BE tissues in that it has only been implemented as a point modality to date. To address this limitation, investigators propose to expand a/LCI to cover more tissue area with each measurement and to incorporate image guidance using optical coherence tomography (OCT), as a “red flag” to help target abnormal tissue for closer interrogation. OCT provides micron scale, cross-sectional tissue images. It can discriminate BE tissues from typical squamous epithelium but has lesser accuracy in detecting dysplasia compared to a/LCI.²¹⁻²⁴ By combining these two imaging modalities, investigators seek to provide a more incisive, clinically useful tool to aid physicians in diagnosis and monitoring of BE patients.

Angle-resolved LCI (a/LCI) and OCT are two imaging technologies that will be integrated into one probe. The purpose of this pilot study is to first utilize optical coherence tomography (OCT) technology alone, delivering it in a form factor that is conducive to upper endoscopy. In the second phase of the study, the optical coherence tomography (OCT) technology will be combined with the angle-resolved LCI (a/LCI) into a multimodal device developed by investigators on a small population of patients in an effort to gather information necessary for continuing development as a screening tool described above.

